8.0 Dosage Modification Based on Adverse Events

If a patient develops an allergic reaction during injection of ^{18}F -DOPA, the patient is not to receive any additional tracer and will not undergo PET imaging and will go off study.

9.0 Ancillary Treatment/Supportive Care: None.

10.0 Adverse Event (AE) Reporting and Monitoring

10.1 Adverse Event Characteristics

CTCAE term (AE description) and grade: The descriptions and grading scales found in the revised NCI Common Terminology Criteria for Adverse Events (CTCAE) version 4.0 will be utilized for AE reporting. All appropriate treatment areas should have access to a copy of the CTCAE version 4.0. A copy of the CTCAE version 4.0 can be downloaded from the CTEP web site (<http://ctep.cancer.gov>).

10.11 Adverse event monitoring and reporting is a routine part of every clinical trial. First, identify and grade the severity of the event using a copy of the CTCAE v4.0. Next, determine whether the event is expected or unexpected (refer to Sections 10.2 and [15.0](#)) and if the adverse event is related to the medical treatment or procedure (see Section 10.3). With this information, determine whether an adverse event should be reported as an expedited report (see Section 10.2) or as part of the routinely reported clinical data. **Important:** All AEs reported via expedited mechanisms must also be reported via the routine data reporting mechanisms defined by the protocol (see [Sections 10.6](#) and [18.0](#)).

Expedited and routine reports are to be completed within the timeframes and via the mechanisms specified in Sections 10.4 and 10.6. All expedited AE reports must also be sent to the local Institutional Review Board (IRB) according to local IRB's policies and procedures.

10.2 Expected vs. Unexpected

- The determination of whether an AE is expected is based on agent-specific adverse event information provided in [Section 15.0](#) of the protocol.
- Unexpected AEs are those not listed in the agent-specific adverse event information provided in [Section 15.0](#) of the protocol.

NOTE: "Unexpected adverse experiences" means any adverse experience that is neither identified in nature, severity, or frequency of risk, in the information provided for IRB review nor mentioned in the consent form.

10.3 Assessment of Attribution

Patients will be observed for adverse events for approximately 15-20 minutes post ^{18}F -DOPA injection by the Nuclear Medicine health professionals administering the scan. Post therapy ^{18}F -DOPA scans will have pre-existing conditions documented prior to ^{18}F -DOPA injection in order delineate causality for pre and post ^{18}F -DOPA AEs.

Patients will be regularly evaluated by a radiation oncology health professional per standard clinical practice throughout their course of external beam radiation therapy.

When assessing whether an adverse event is related to a medical treatment or procedure, the following attribution categories are utilized:

Definite - The adverse event *is clearly related* to PET scanning and ¹⁸F-DOPA injection

Probable - The adverse event *is likely related* to PET scanning and ¹⁸F-DOPA injection

Possible - The adverse event *may be related* to PET scanning and ¹⁸F-DOPA injection

Unlikely - The adverse event *is doubtfully related* to PET scanning and ¹⁸F-DOPA A injection

Unrelated - The adverse event *is clearly NOT related* to PET scanning and ¹⁸F-DOPA injection

Definite - The adverse event *is clearly related* to RT dose escalation

Probable - The adverse event *is likely related* to RT dose escalation

Possible - The adverse event *may be related* to RT dose escalation

Unlikely - The adverse event *is doubtfully related* to RT dose escalation

Unrelated - The adverse event *is clearly NOT related* to RT dose escalation

Events determined to be possibly, probably or definitely attributed to a medical treatment suggest there is evidence to indicate a causal relationship between the drug/treatment and the adverse event.

10.31 AEs Experienced Utilizing Investigational Agents and Commercial Agent(s) on the SAME Arm

NOTE: When a commercial agent(s) is (are) used on the same treatment arm as the investigational agent/intervention (also, investigational drug, biologic, cellular product, or other investigational therapy under an IND), the entire combination (arm) is then considered an investigational intervention for reporting-

Routine Reporting

- Routine AE reporting for Phase 1 and Phase 2 clinical studies using an investigational agent /intervention in combination with a commercial agent is stated in the protocol. See [Section 10.6](#).
- Routine AE reporting for Phase 3 clinical studies using an investigational agent/intervention and a commercial agent in combination must be reported as defined by the general guidelines provided by sponsors, Groups, Cancer Centers, or Principal Investigators. See [Section 10.6](#).

Expedited Reporting

- An AE that occurs on a combination study must be assessed in accordance with the guidelines for investigational agents/interventions in Section 10.4, and where indicated, an expedited report must be submitted.
- An AE that occurs prior to administration of the investigational agent/intervention must be assessed as specified in the protocol. In general, only Grade 4 and 5 AEs that are unexpected with at least possible attribution to the commercial agent require an expedited report. Refer to [Section 10.4](#) for specific AE reporting requirements or exceptions.
- Commercial agent expedited reports must be submitted to the FDA via MedWatch.

- An investigational agent/intervention might exacerbate the expected AEs associated with a commercial agent. Therefore, if an expected AE (for the commercial agent) occurs with a higher degree of severity, expedited reporting is required. The clinical investigator must determine severity.

10.4 Expedited Reporting Requirements for IND/IDE Agents

Phase 1 and Early Phase 2 Studies: Expedited Reporting Requirements for Adverse Events that Occur on Studies under an IND/IDE within 30 Days of the Last Administration of the Investigational Agent/Intervention^{1, 2}

FDA REPORTING REQUIREMENTS FOR SERIOUS ADVERSE EVENTS (21 CFR Part 312) NOTE: Investigators MUST immediately report to the sponsor ANY Serious Adverse Events, whether or not they are considered related to the investigational agent(s)/intervention (21 CFR 312.64) An adverse event is considered serious if it results in ANY of the following outcomes:
 
 1) Death 2) A life-threatening adverse event 3) An adverse event that results in inpatient hospitalization or prolongation of existing hospitalization for ≥ 24 hours 4) A persistent or significant incapacity or substantial disruption of the ability to conduct normal life functions 5) A congenital anomaly/birth defect. 6) Important Medical Events (IME) that may not result in death, be life threatening, or require hospitalization may be considered serious when, based upon medical judgment, they may jeopardize the patient or subject and may require medical or surgical intervention to prevent one of the outcomes listed in this definition. (FDA, 21 CFR 312.32; ICH E2A and ICH E6). 		

ALL SERIOUS adverse events that meet the above criteria MUST be immediately reported to the sponsor within the timeframes detailed in the table below.
		
Hospitalization	Grade 1 and Grade 2 Timeframes	Grade 3-5 Timeframes
Resulting in Hospitalization ≥24 hrs	7 Calendar Days	24-Hour, 3 Calendar Days
Not resulting in Hospitalization ≥24 hrs	Not required	

NOTE: Protocol specific exceptions to expedited reporting of serious adverse events are found in Section 10.41 of the protocol.
 
Expedited AE reporting timelines are defined as:
 
 ○ "24-Hour; 3 Calendar Days" - The AE must initially be reported within 24 hours of learning of the AE, followed by a complete expedited report within 3 calendar days of the initial 24-hour report. ○ "7 Calendar Days" - A complete expedited report on the AE must be submitted within 7 calendar days of learning of the AE. 		

¹Serious adverse events that occur more than 30 days after the last administration of investigational agent/intervention and have an attribution of possible, probable, or definite require reporting as follows: Expedited 24-hour notification followed by complete report within 3 calendar days for:
 
 • All Grade 3, 4, and Grade 5 AEs 
Expedited 7 calendar day reports for:
 
 • Grade 2 AEs resulting in hospitalization or prolongation of hospitalization 
² For studies using PET or SPECT IND agents, the AE reporting period is limited to 10 radioactive half-lives, rounded UP to the nearest whole day, after the agent/intervention was last administered. Footnote "1" above applies after this reporting period. For ¹⁸FDOPA, 10 radioactive half-lives is 18.3 hours or 1 whole day.
 
Effective Date: May 5, 2011
		

NOTE: Use [REDACTED]

Mayo Clinic Cancer Center (MCCC) Institutions:

Provide copies of all serious events, regardless of drug relatedness to:

[REDACTED] (¹⁸F-DOPA IND sponsor) at [REDACTED] and [REDACTED]

These emails will be managed by the SAE, IND and Safety Reporting Coordinators.

10.41 **Special Situations for Expedited Reporting**

Exceptions to Expedited Reporting: EXPECTED Serious Adverse Events

An expedited report may not be required for specific Grade 1, 2 and 3 Serious Adverse Events where the AE is **EXPECTED**. Any protocol specific reporting procedures **MUST BE SPECIFIED BELOW** and will supersede the standard Expedited Adverse Event Reporting Requirements: **Hospitalizations for reasons deemed to be disease related will not be reported.**

PET scanning, PET tracer injection and dose escalation are the only procedures unique to this study. All other aspects of radiation therapy and follow-up are part of standard brain cancer treatment. Consequently, only adverse events *possibly, probably, or definitely* related to ¹⁸F-DOPA PET administration or radiotherapy will be graded and reported in this protocol. All other toxicities associated with other components of conventional brain cancer treatment (e.g. hematological events resulting from chemotherapy) will not be graded or reported as part of this protocol.

System Organ Class (SOC)	Adverse event/ Symptoms	CTCAE Grade at which the event will not be expeditedly reported.
General disorders and administration site conditions	Fatigue	≤Grade 3
Immune system disorders	Allergic Reaction	≤Grade 3
Nervous system disorders	Central nervous system necrosis	≤Grade 3
Nervous system disorders	Vasovagal reaction	≤Grade 3
Injury, poisoning and procedural complications	Bruising	≤Grade 3
Skin and subcutaneous tissue disorders	Rash maculo-papular	≤Grade 3

Report any clinically important increase in the rate of a serious suspected adverse reaction over that which is listed in the protocol or investigator brochure as an expedited.

Report an expected event that is greater in severity or specificity than expected as an expedited event.

10.5 Other Required Reporting

10.51 Persistent or Significant Disabilities/Incapacities

Any AE that results in persistent or significant incapacity or substantial disruption of the ability to conduct normal life functions (formerly referred to as disabilities), congenital abnormalities or birth defects, must be reported immediately if they occur at any time following treatment with an agent under an IND/IDE since they are considered to be a serious AE and must be reported to the sponsor as specified in 21 CFR 312.64(b).

10.52 Death

The reporting period for ¹⁸F-DOPA for this study is 1 day.

The reporting period for radiation dose escalation for this study is 30 days.

Any death occurring within 1 day after ¹⁸F-DOPA agent was last administered or within 30 days of the last radiation dose, regardless of attribution requires expedited reporting within 24-hours.

Any death occurring greater than 1 day after the last ¹⁸F-DOPA agent was administered with an attribution of possible, probable, or definite requires expedited reporting within 24-hours.

Any death occurring greater than 30 days after the last radiation dose was administered with an attribution of possible, probable, or definite requires expedited reporting within 24-hours.

Reportable categories of Death

- Death attributable to a CTCAE term.
- Death Neonatal: A disorder characterized by cessation of life during the first 28 days of life.
- Death NOS: A cessation of life that cannot be attributed to a CTCAE term associated with Grade 5.
- Sudden death NOS: A sudden (defined as instant or within one hour of the onset of symptoms) or an unobserved cessation of life that cannot be attributed to a CTCAE term associated with Grade 5.
- Death due to progressive disease should be reported as **Grade 5 “Neoplasms benign, malignant and unspecified (incl cysts and polyps) – Other (Progressive Disease)”** under the system organ class (SOC) of the same name. Evidence that the death was a manifestation of underlying disease (e.g., radiological changes suggesting tumor growth or progression: clinical deterioration associated with a disease process) should be submitted.

10.53 Secondary Malignancy

- A **secondary malignancy** is a cancer caused by treatment for a previous malignancy (e.g., treatment with investigational agent/intervention, radiation or chemotherapy). A secondary malignancy is not considered a metastasis of the initial neoplasm.
- All secondary malignancies that occur following treatment with an agent under an IND/IDE will be reported. Three options are available to describe the event:

- Leukemia secondary to oncology chemotherapy (e.g., Acute Myelocytic Leukemia [AML])
- Myelodysplastic syndrome (MDS)
- Treatment-related secondary malignancy
- Any malignancy possibly related to cancer treatment (including AML/MDS) should also be reported via the routine reporting mechanisms outlined in each protocol.

10.54 Second Malignancy

A second malignancy is one unrelated to the treatment of a prior malignancy (and is NOT a metastasis from the initial malignancy). Second malignancies require ONLY routine reporting-

10.6 Required Routine Reporting

Adverse events related to PET scanning and PET tracer injection to be graded if detected during observation post injection, or if noted within 24-hour post PET tracer injection per the CTCAE v4.0 grading. Adverse events related to dose escalation will be graded at baseline, assessed during RT and reported at the end of RT, and during every clinically indicated MR follow-up during Active Monitoring until progression.

Category (CTCAE SOC)	Adverse event/Symptoms	Baseline	Post injection assessment ¹	Active Monitoring
General disorders and administration site conditions	Fatigue	X		X
Immune system disorders	Allergic reaction		X	
Nervous system disorders	Central nervous system necrosis			X
Nervous system disorders	Vasovagal reaction		X	
Injury, poisoning and procedural complications	Bruising	X	X	
Skin and subcutaneous tissue disorders	Rash maculo-papular	X	X	

1. This assessment should occur approximately 15-20 minutes post injection (after scan is completed).

10.61 Additional instructions:

Submit via appropriate MCCC Case Report Forms (i.e., paper or electronic, as applicable) the following AEs experienced by a patient and not specified in Section 10.6:

- 10.611 Grade 2 AEs deemed *possibly, probably, or definitely* related to the study treatment or procedure.
- 10.612 Grade 3 and 4 AEs regardless of attribution to the study treatment or procedure.
- 10.613 Grade 5 AEs (Deaths) (See [Section 10.52](#))

10.62 Late Occurring Adverse Events:

Refer to the instructions below and in the Forms Packet (or electronic data entry screens, as applicable) regarding the submission of late occurring AEs following completion of the Active Monitoring Phase (i.e., compliance with Test Schedule – see [Section 4.0](#)).

Toxicity will be monitored continuously as each patient is accrued and follow-up data are accumulated. Acute radiation therapy and chemotherapy toxicities will be graded using Common Terminology Criteria for Adverse Events (CTCAE) v4.0 (available at <http://ctep.cancer.gov>). Late toxicities will be reported using the RTOG/EORTC late toxicity criteria [71].

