4.0 Test Schedule

Tests and procedures	Active Monitoring				
	Baseline				Until PD or patient refusal
	≤21 days prior to registration	Cycle 1 Pre-RT Scans	Cycle 1 RT	Cycle 2 Post RT Scans ⁵ ≤42 days after RT	At every clinically indicated follow-up MR scan (end of each new cycle)
Physical exam, wt, ECOG PS	X				
Neuro history and exam	X			X	X
MMSE ⁴		X ¹²		X	X
CT simulation for radiotherapy planning	X ^{8,9}				
Pregnancy test		X ^{1,R}		X ^{1,R}	X ^{1,R}
¹⁸ F-DOPA-PET ^R		X ⁸		X	X ³
MRI with contrast/ RANO Assessment		X ^{6,8}		X	X ³
Advanced MRI		X ^{7,8}		X	X ³
¹⁸ F-DOPA adverse event assessment		X ²		X ²	X ²
Adverse event assessment ¹¹ (See Section 10.3)	X		X ¹⁰	X	X
QOL assessment ⁴		X ¹²		X	X
Concurrent Steroids and Anticonvulsants		X ¹²		X	X
MGMT Methylation Status	X ¹³				

1. For women of childbearing potential only. Must be done ≤48 hours prior to injection of study drug. Note: For a positive pregnancy test prior to the pre-RT ¹⁸F-DOPA injection the patient will not undergo the ¹⁸F-DOPA PET scan and will instead be taken off study with no follow-up. For any post-RT ¹⁸F-DOPA injection, the patient will not undergo the ¹⁸F-DOPA PET scan and will instead move to event monitoring.
2. ¹⁸F-DOPA post-injection assessment: done approximately 15-20 minutes post injection of ¹⁸F-DOPA and if AE observed a second AE assessment is required ≤24 hours post injection.
3. All follow-up serial imaging after initial treatment until progression up to 5 years. Note a typical grade IV follow-up schedule will include follow-up scans every 2 months for the first year after

radiation therapy, every 3 months for the second year, every 4 months for the third year, every 6 months after that. The actual timing of the follow-up scans for an individual patient will be per the clinician's discretion, e.g. if the clinician suspects possible progression, they may schedule more frequent follow-up imaging. While it is extremely unlikely (as current time to progression is 6 to 9 months), if a grade IV patient did not progress for 5 years, they may have up to 16 follow-up visits.

4. Patient will complete a maximum of 6 post-baseline QOL/MMSE evaluations
 5. Post RT scans to occur 3 to 6 weeks after RT is complete, to coordinate with first follow-up appointment
 6. Pre-treatment measurement

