Determine acute and late effect toxicity after radiotherapy treatment targeting dose escalated volumes defined to include high ^{18}F -DOPA PET uptake. The rate of acute and late treatment-related toxicities for newly diagnosed high-grade glioma patients treated with ^{18}F -DOPA PET image-guided dose escalation will be determined, with acute RT toxicities graded using Common Terminology Criteria for Adverse Events (CTCAE) v4.0 (available at <http://ctep.cancer.gov>), and late toxicities reported using the RTOG/EORTC late toxicity criteria [71]. Patients will be considered evaluable for adverse events if they receive ^{18}F -DOPA PET or ^{18}F -DOPA PET image-guided dose escalation RT.

16.326 Compare confirmed-progression free survival at 12 months for Grade IV MGMT-methylated patients after radiation therapy targeting volumes designed with both ^{18}F -DOPA PET and conventional MR image information with historical controls from Mayo Clinic Rochester patients, including those on clinical trials.

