18.13 Follow-up Material(s)

CRF	Event Monitoring Phase ¹		
	q. yearly for 5 years	At PD	Death
Event Monitoring Form	X	X	X
CD/DVD Radiology Imaging		X ²	

1. If a patient is still alive 5 years after registration, no further follow-up is required.
2. If patient leaves Mayo Clinic, please obtain imaging in DICOM format from local MD. The study will pay for costs associated with providing copies of the imaging to Mayo Clinic. See [Appendix VI](#) for details. Imaging CDs (MRI) must be de-identified. The surface of the CD should be labeled with MC1374, the patient's Mayo Clinic identification number (or initials (L, F, M) and birth date) and the scan date only.
Mail CDs to: Mayo Clinic, Attn: QAS Study MC1374, [REDACTED]
[REDACTED] Rochester, MN [REDACTED].

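### Scheduled grading of dose-escalation toxicity stops when a patient leaves Active Monitoring, and the late-toxicity rate has no time point or allowance for unequal follow-up, so late toxicity is likely to be underestimated

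*Combined protocol and SAP*

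**What the plan says.** Goal 2.24 is to determine acute and late toxicity after dose-escalated radiotherapy. The provisions that bear on it are these.

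- **Scheduled grading.** Section 10.6 runs it "during every clinically indicated MR follow-up during Active Monitoring until progression". The last column of the Section 4.0 test schedule has the same limit.
- **Leaving Active Monitoring.** Under Sections 13.4 and 13.5 a patient moves to event monitoring at confirmed progression (radiologic and clinical, more than 3 months after radiotherapy) or on declining further PET scans.
- **Forms.** The Radiation Therapy Adverse Event Form, which carries the late-toxicity footnote, is only in the Active-Monitoring table of Section 18.12. Section 18.13 lists the "Event Monitoring Form" (yearly, at progression and at death) and imaging.
- **After Active Monitoring.** Section 10.62 refers to instructions in the text and in a Forms Packet "regarding the submission of late occurring AEs following completion of the Active Monitoring Phase". The text supplied there says that toxicity is monitored continuously and names the scales: "Late toxicities will be reported using the RTOG/EORTC late toxicity criteria".
- **Serious events.** Section 10.4, footnote 1, keeps late serious events reportable if at least possibly related. Section 10.52 does the same for "Any death occurring greater than 30 days after the last radiation dose was administered with an attribution of possible, probable, or definite". Section 10.41 lists "Central nervous system necrosis" up to Grade 3 among events exempt from expedited reporting.
- **Analysis.** Section 16.325 says "The rate of acute and late treatment-related toxicities for newly diagnosed high-grade glioma patients treated with" PET-guided escalation will be determined. A patient is evaluable after either the PET scan or the escalated radiotherapy.

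**The concern.** Late radiation injury takes time to appear, and this population progresses early: Section 4.0, note 3, says "as current time to progression is 6 to 9 months". If scheduled collection ends at progression, many patients have only a few months in which a late event can be recorded. Those who progress first, which here points to the un-methylated patients, have the least.

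Section 16.325 does not allow for this. A rate with no time point gives the same weight to a patient watched for four months as to one watched for three years. Patients who had the PET scan but no escalated radiotherapy can enter the denominator without being at risk of the boost's late effects. Both features push the estimate down and make escalation look safer.

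The estimate answers a named secondary goal. The stopping rule in Section 16.42, which counts Grade 3 or 4 irreversible CNS toxicity against 10% of enrolled patients, draws on the same data.

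**Working it through.** The plan states no figure for late toxicity or its capture, so there is none to reproduce. The check has two parts.

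**1. Which events have a route into the data after Active Monitoring**

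| Event after confirmed progression | Scheduled form | Other route |
|---|---|---|
| Related death | Event Monitoring Form at death | Expedited (10.52) |
| Related serious event, Grade 3 to 5 | None listed | Expedited (10.4, footnote 1), and by 10.11 also routine |
| Persistent or significant incapacity | None listed | Reportable at any time (10.51) |
| CNS necrosis up to Grade 3 | None listed | Exempt from expedited reporting (10.41); 10.62 without a schedule |
| Other Grade 3 or 4; related Grade 2 | None listed | 10.61, without a visit or form date |
| Fatigue and other lower-grade, non-serious events | None listed | 10.62 at most |

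Section 10.61 covers events not already specified in Section 10.6. CNS necrosis is specified there, for Active Monitoring only, so on its wording 10.61 does not fill that row.

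**2. How much could be missed if nothing were collected after progression**

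Inputs from the documents: time to progression 6 to 9 months (Section 4.0, note 3), and 6-month confirmed-progression-free proportions of 60% (null) and 72.5% (alternative) in Section 16.21. With exponential times, the median is 6·ln 2/(−ln p), which gives 8.1 months for p = 0.60 and 12.9 months for p = 0.725. The first lies inside the stated 6 to 9 months. The share still progression-free is 2^(−t/median):

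| Median (months) | At 12 months | At 24 months |
|---|---|---|
| 6 | 25% | 6% |
| 8.1 | 36% | 13% |
| 9 | 40% | 16% |
| 12.9 | 53% | 28% |

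Assumptions, none of them given in the documents: radiotherapy ends 2.5 months after surgery; late onset begins 3 months after that (c = 5.5) and is then exponential with median 3 to 18 months; median survival after progression is 6 to 9 months; all times are independent. Rates are λ = ln 2/median for progression (P), death after progression (D) and onset (T).

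- A(λ) = exp(−λc)·λT/(λT + λ)
- Onset before progression: A(λP)
- Onset while alive: [λD·A(λP) − λP·A(λD)]/(λD − λP)
- Share missed: 1 − (onset before progression)/(onset while alive)

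*Lowest case for a 6 to 9 month median* (progression 9, survival 6, onset 3): A(λP) = 0.6547 × 0.75 = 0.4910; A(λD) = 0.5297 × 0.6667 = 0.3532; while alive = 3 × 0.4910 − 2 × 0.3532 = 0.767; missed = 1 − 0.4910/0.767 = **36%**.

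*Highest case* (progression 6, survival 9, onset 18): A(λP) = 0.5297 × 0.25 = 0.1324; A(λD) = 0.6547 × 0.3333 = 0.2182; while alive = 3 × 0.2182 − 2 × 0.1324 = 0.390; missed = 1 − 0.1324/0.390 = **66%**.

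The same formula gives 39% to 56% at a median of 8.1 months and 26% to 41% at 12.9 months.

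*As a rate.* Take a constant hazard from month 3 that gives 20% by month 24, h = −ln(0.8)/21 = 0.0106 per month, with c = 3 and an 8-month median survival after progression. Onset before progression is 0.7071 × 0.0106/(0.0106 + 0.1155) = 6.0% at a 6-month median and 0.7937 × 0.0106/(0.0106 + 0.0770) = 9.6% at 9 months. Followed to death, the figures are 15.8% and 19.2%.

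**The case against.** The strongest reply is that collection does not stop at progression. Section 10.62 is expressly about the period after Active Monitoring and calls monitoring continuous. Related serious events, incapacity and related deaths have no cut-off at progression, and Section 10.11 brings every expedited event into the routine data. The Forms Packet is not in the documents, and Section 18.13 gives form names, not contents, so the Event Monitoring Form may already hold a toxicity item. All of this stands. A reader might infer that toxicity is collected only until progression; the text does not support that. What remains is that no schedule or toxicity form is stated, and that CNS necrosis up to Grade 3 is reached neither by expedited reporting nor, on its wording, by Section 10.61.

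The model also ends observation too soon. Active Monitoring ends at confirmed progression, and Section 11.416 back-dates the progression date to the preliminary finding. Bevacizumab alone does not count as progression. Suppose observation lasts one 2-month scan interval longer. The missed share is then exp(−2λD) times the gap between the alive and before-progression terms at c = 3.5, divided by the alive term at c = 5.5. The range falls from 36–66% to 26–58%. The loss is smaller but still material.

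Finally, ending attribution-based grading before salvage therapy confuses the cause is defensible, and the endpoint is descriptive. That supports reporting the two periods separately. It does not support leaving the second without a schedule.

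**Conclusion.** The point holds as a gap in scheduled collection and an unspecified estimator. Late toxicity is likely to be underestimated, chiefly through non-serious events and CNS necrosis up to Grade 3.

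The size is conditional. Roughly one-third to two-thirds of late events would be missed if nothing were collected after a progression time with a median of 6 to 9 months. The share is lower if progression is delayed as the trial hopes, if confirmation extends observation, or once the serious-event rules are credited. Onset and survival after progression are assumed, and the 6 to 9 month figure is not tied to confirmed progression.

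Three stronger readings are tempting and not supported:

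- That most late toxicity would go unrecorded: the share crosses one half within the assumed ranges.
- That the plan specifies a crude proportion: Section 16.325 names no estimator.
- That a planned conclusion of no added late toxicity would fail: that expectation is background in Section 1.4, while goal 2.24 and Section 16.325 only determine toxicity.

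This should be changed because the remedy is cheap and the error has a known direction.

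**What to change.** **Collection.** Reconcile Sections 10.6, 10.62 and 18.13. Add one late CNS toxicity and necrosis item (grade, onset date, attribution) to the existing Event Monitoring Form, completed at progression and at each later contact already scheduled, yearly and at death. Apply it also to patients who leave Active Monitoring by declining PET scans. If the Forms Packet already has such an item, cite it in Section 10.62 and list it in Section 18.13.

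**Analysis.** In Section 16.325, report late radiotherapy toxicity only among patients who received dose-escalated radiotherapy. Use cumulative incidence from radiotherapy at fixed times, with death as a competing event and numbers at risk, split into events before and after progression. If collection does stop at progression, treat progression as a competing event too and say that the estimate covers only the period before it. Keep the PET-or-radiotherapy denominator for tracer events.

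**Cost.** One form item and a few lines of analysis text, with no change to treatment or visits. Attribution is less certain after salvage treatment, which is why the split is needed. Yearly contact dates onset only approximately unless the onset date is recorded.
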